## 7 STATISTICAL METHODOLOGY

### 7.1 General Considerations

In general, descriptive statistics are defined for continuous variables as number of subjects (n), mean, standard deviation, minimum, median and maximum, and as frequency and percentage for categorical variables.

In summary and analysis tables of continuous variables, the minimum and maximum statistics will be presented to the same number of decimal places as the original data. The mean, median, quartile, and 2-sided 95% confidence interval (CI) will be presented to 1 more decimal place than the original data. The standard deviation and standard error will be presented to 2 more decimal places than the original data.

In summary tables of categorical variables, the number of non-missing observations and percentages will be presented. Unless specified otherwise, percentages by categories will be based on the number of subjects with no missing data. For categorical variables with missing values, an additional level of the variable will be added to the summary as “Missing” and the frequency will be displayed but no percentage.

Efficacy analysis will be conducted on the FAS and PPS. The primary analysis set for efficacy analyses will be the FAS. The PPS will be used to assess the robustness of the results from the statistical tests based on the FAS. Summaries based on FAS and PPS will be presented by planned treatment group, unless specifically stated otherwise. Safety analysis and other summaries based on SAF will be presented by actual treatment received.

Unless otherwise specified, all statistical testing will be conducted using two-sided tests with a significance level of 0.05.

All statistical analyses will be performed using SAS® v9.3 or higher. Specifications for table, figures, and data listing formats can be found in the TLF specifications for this study.

For the definition of subgroups of interest please refer to section 7.8.

## 7.2 Study Population

### 7.2.1 Disposition of Subjects

The following subject data will be presented:

- Number of subjects with informed consent, discontinued before randomization, randomized (overall only);
- Number of subjects randomized in each analysis set, by treatment group and overall;
- Number and percentage of subjects that received study drug, by treatment group and overall;
- Number and percentage of subjects completed and discontinued treatment, by primary reason for treatment discontinuation for randomized subjects, by treatment group;
- Number and percentage of subjects completed and discontinued the 1 year follow-up period, by primary reason for discontinuation, by treatment group and overall;
- Number and percentage of subjects completed and discontinued the continued follow-up period, by primary reason for discontinuation, by treatment group and overall;
- Number and percentage of subjects excluded from PPS by reason for exclusion defined in section 5.2.1, by treatment group and overall.

### 7.2.2 Protocol Deviations

Protocol deviations will be reported in data listing(s) by site, treatment group and subject. And will be presented by Syneos Health no later than the data review meeting (DRM) in order to adjudicate deviations prior to database lock. All protocol deviations will be reviewed and categorized prior to the database lock. A major deviation has an impact on subject safety, may substantially alter risks to subjects, may have an effect on the integrity of the study data, or may affect the subject's willingness to participate in the study. A minor deviation is a minor or administrative departure from the protocol without prior consent and does not have an impact on subject safety, nor an effect on the integrity of the study data.

### 7.2.3 Demographic and Other Baseline Characteristics

Demographic data (age, sex, race, and ethnicity) will be summarized by treatment group and overall for the FAS. Descriptive statistics will be included for continuous endpoints and frequency and percentage for categorical endpoints.

Subject characteristics of height (in cm), weight (in kg), BMI at screening, substance use/tobacco history, 12-lead electrocardiogram interpretations, biopsy targeting method (mpMRI vs non-mpMRI), prostate cancer risk group (low vs. intermediate) and the incidence of relatives with prostate cancer and their age at diagnosis will be summarized with descriptive statistics by treatment group and overall for the FAS.

Data listings will be presented for the demographic and baseline characteristic data.

#### **7.2.4 Previous and Concomitant Medications**

Prior and concomitant medications will be coded according to the World Health Organization (WHO) DDE version March 2016. Prior medications are non-study medications that are recorded and stopped prior to the screening visit date. Prior medications will be exclusively reported in data listings. Concomitant medications are those that start on or after the screening visit date. Non-medication therapies will not be coded and summaries will be limited to overall use, reason for use, and radiation details.

Concomitant medications will be summarized descriptively for each treatment group and overall by therapeutic subgroup (ATC 2nd level), chemical subgroup (ATC 4th level) and preferred name by treatment group for the FAS and displayed in data listings. Subjects taking the same medication multiple times will be counted once per medication and investigational period. A medication that can be classified into several chemical and/or therapeutic subgroups is presented in all chemical and therapeutic subgroups.

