**Table 3**

ICH Category	ICH Definition	ENACT Interpretation
PD [1]	Subjects who entered the study even though they did not satisfy the entry criteria	

• Subject randomized without meeting the inclusion/exclusion criteria

• Subject missed assessment(s)/procedure(s) impacting eligibility for study participation

PD [2]	Subjects who developed withdrawal criteria during the study but were not withdrawn	

• Subject developed withdrawal criteria during the study and was not withdrawn

PD [3]	Subjects who received the wrong or incorrect treatment dose	

• Subject received wrong treatment or incorrect dose, or patient taking commercial Xtandi instead of study-labeled enzalutamide, also consuming drug that should have been quarantined

PD [4]	Subjects who received excluded concomitant treatment	

• Subject took medication prohibited by the protocol

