## **7.10 Handling of Missing Data, Outliers, Visit Windows, and Other Information**

### **7.10.1 Missing Data**

As a general principle, no imputation of missing data will be done. Exceptions are the start and stop dates and relationship of AEs and CMs and visit windows.

All analysis will be based on available data to summarize safety and efficacy results.

However, a conservative approach to partial dates and missing adverse event relationships will be as follows:

- For survival analyses, if a subject's death month and year are provided but the day is missing, the day will be set to the first day of the month, unless other qualifying study data support survival until a later date in the same month.
- For subjects in the enzalutamide arm, adverse events with partial dates with the same month and year as the first dose date of study drug will be considered as treatment-emergent adverse events.
- For subjects in the enzalutamide arm, if an adverse event's relationship is missing, it will be assumed to be related.
- For subjects in the enzalutamide arm, if the AE or CM start day is missing, then impute the 1st of the month unless month and year are the same as the month and year of first dose of study drug, then impute AE/CM start date with the first dose date. If the start month and day are both missing, then impute 01JAN unless the year is the same as first dose date, then impute AE/CM start date with the first dose date. If the entire start date is missing, then no imputation will be performed, but the AE will be considered treatment-emergent.
- For subjects on active surveillance, if the AE or CM start day is missing, then impute the 1st of the month unless month and year are the same as the month and year of randomization, then impute AE/CM start date with the randomization date. If the start month and day are both missing, then impute 01JAN unless the year is the same as randomization date, then impute AE/CM start date with the randomization date. If the entire start date is missing, then no imputation will be performed, but AE will be considered to have occurred on or after randomization date.

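### Medicines started before screening and still taken at screening are neither prior nor concomitant under SAP Section 7.2.4, so they drop out of the by-arm medication table and both listings as defined

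*SAP*

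**What the plan says.** Section 7.2.4 gives both definitions in adjacent sentences. For prior use: "Prior medications are non-study medications that are recorded and stopped prior to the screening visit date". For concomitant use: "Concomitant medications are those that start on or after the screening visit date".

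The class decides where a medicine is reported. For the prior class, "Prior medications will be exclusively reported in data listings". The concomitant class receives the table: "Concomitant medications will be summarized descriptively for each treatment group and overall by therapeutic subgroup (ATC 2nd level), chemical subgroup (ATC 4th level". That table is on the FAS, goes down to the individual drug, and is accompanied by listings.

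Three other places touch on the subject:

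- Table 2 (Schedule of Assessments) has concomitant medication recorded from screening onward.
- Section 7.10.1 imputes incomplete start and end dates of medicines.
- Table 3 makes the use of a prohibited medicine a ground for possible exclusion from the PPS: "Subject took medication prohibited by the protocol".

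Section 8, which lists departures from the protocol, does not mention the medication classes in its readable text.

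**The concern.** One class is bounded by the stop date and the other by the start date, so the two need not meet. The space between them is a medicine begun before screening and not yet stopped when the subject was screened. That describes any continuing treatment a subject brings into the study.

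At stake is the description of co-medication in an open-label comparison of enzalutamide with active surveillance. A reader who wants to know what else each arm was taking has one planned table to look at. As written, it shows a short course begun and finished during the screening period, but not a medicine taken every day from before screening through the treatment year.

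**Working it through.** The SAP states no figure on this point, so there is nothing to reproduce. The check is whether the two rules in Section 7.2.4 cover every case.

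**Rules.** Let V be the screening visit date, S the start date and E the stop date (no E if ongoing).

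- Prior: E < V.
- Concomitant: S ≥ V.
- Unclassified: S < V and not (E < V).

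**All orderings of S and E around V:**

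| Start | Stop | Prior? | Concomitant? | As written | With the added clause |
|---|---|---|---|---|---|
| before V | before V | yes | no | prior | prior |
| before V | on V | no | no | **neither** | concomitant |
| before V | after V | no | no | **neither** | concomitant |
| before V | ongoing | no | no | **neither** | concomitant |
| on V | any later date | no | yes | concomitant | concomitant |
| after V | stopped | no | yes | concomitant | concomitant |
| after V | ongoing | no | yes | concomitant | concomitant |

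As written, 3 of 7 orderings have no class, 4 have exactly one, and none has two. With the added clause (S ≥ V, or S < V and not E < V), all 7 have exactly one. The class then depends on the stop date alone: stopped before V is prior, and everything else is concomitant.

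**Does another section close the gap?** Section 7.10.1 is the only candidate. It says "if the AE or CM start day is missing, then impute the 1st of the month unless month and year are the same as" those of first dose (randomization for active surveillance), in which case that date is used. A corresponding rule covers a missing month. Three things follow:

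1. A complete start date is never altered, so a medicine with a complete pre-screening start date stays unclassified.
2. A partial start date in the same month as first dose or randomization (or the same year, if the month is missing too) is moved to that date. The medicine then counts as concomitant. Other partial dates go to the first of the month or of the year and usually remain in the gap. Two subjects on the same medicine since the same day can therefore be treated differently because one date was recorded less completely.
3. If the whole start date is missing, nothing is imputed. Section 7.10.1 then gives a default for adverse events but none for medicines.

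The imputation rules therefore catch some of these medicines by accident. No section provides a third class.

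**The case against.** The literal gap cannot be disputed. The case on the other side is about what follows from it, and most of that case stands.

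- **The data are not lost.** Medicines are recorded from screening onward, so the gap affects how they are classified and reported. It can be repaired from the database. This stands. So does the point that not every medicine ongoing at screening is left out, because some with partial start dates are moved into the concomitant class.
- **Prohibited medicines are not missed.** A reader might infer from Table 3 that prohibited-medication deviations would escape notice. The SAP does not support that. Sections 5.2.1 and 7.2.2 have documented deviations reviewed and categorized before database lock, and the Table 3 criterion refers neither to the Section 7.2.4 classes nor to a start date.
- **No inference depends on it.** Concomitant medication is not a covariate in the Cox model (7.4.1), the logistic models (7.4.1.1, 7.4.2.1) or the repeated-measures model (7.4.2.3), and it does not define a subgroup (7.8). The table belongs to the study-population section, not to Section 7.5. Any bearing on the reading of safety results is indirect.
- **The programmers may apply the usual rule anyway.** They may, but the SAP does not say so. A table produced by its text would be wrong, and one produced by the usual rule would depart from the plan without explanation. This objection does not remove the point.

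**Conclusion.** Wrong as written, with descriptive consequences only. Every medicine with a complete start date before screening that was still in use at screening is outside both classes. It is therefore outside the one by-arm table of non-study medication and outside both listings as defined.

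It is tempting to go further and say that the table omits most long-term medication. The SAP gives no count of medicines or of subjects taking them at entry, so no proportion can be supported. Long-term medicines begun at or after screening are included.

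The conclusion rests on one assumption: that Section 7.2.4 is applied as it reads. The primary and secondary efficacy results and the adjudication of protocol deviations are unaffected.

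**What to change.** In Section 7.2.4, keep the screening visit as the cut-off and leave the prior definition unchanged. Extend the concomitant definition with one clause, for example: a medicine is concomitant if it began on the day of the screening visit or later, or if it began earlier and had not been stopped before that day (still ongoing, or stopped that day or afterwards). The two classes are then exhaustive and do not overlap. Because class then turns only on the stop date, incomplete start dates no longer affect it.

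Moving the cut-off to first dose is not needed and would open another gap. The table is on the FAS, which is all randomized subjects (Section 5.1), and Section 8 allows for subjects randomized to enzalutamide who leave before taking any dose. They would have no date against which to classify their medicines.

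The cost is one clause in the SAP and a check that the table and listing programs follow it. No new data are needed. Section 1 allows SAP revisions up to database hard lock. After that, the change would have to be justified in the clinical study report.

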#### **7.2.5 Medical and Disease Histories**

Medical history including cancer (disease history), non-cancer history, and prior surgical procedures will be summarized by treatment group and overall for the FAS and coded using the Version 23.0 of the Medical Dictionary for Regulatory Activities (MedDRA) to system organ class and preferred term. The dictionary will be updated once every two years pending sponsor decision. If a subject experienced more than one medical condition within a system organ class, the subject will be counted once under that system organ class. If a subject had more than one count for a particular preferred term, the subject will be counted once under that preferred term.

Disease history data of time since initial diagnosis, time since histological diagnosis and incidence of Primary Gleason Pattern (at initial diagnosis), Secondary Gleason Pattern (at initial diagnosis), Total Gleason Score (at initial diagnosis), Clinical Tumor Stage (at initial diagnosis), Clinical Lymph Node Stage (at initial diagnosis), distant metastasis, prostate cancer-related biomarker testing done (from time of diagnosis until screening) will be summarized by descriptive statistics by treatment group and overall for the FAS.

Data listings will be presented for the medical and surgical histories and disease history.

## **7.3 Study Drugs**

### **7.3.1 Exposure**

Active treatment for prostate cancer and type of therapies will be assessed at Randomization and every study visit thereafter until month 24 and unscheduled. The following information will be presented by treatment group for the FAS:

- Descriptive statistics for cumulative amount of drug that a subject was exposed, and
- Number and percent of subjects with dose decreases, increases or interruptions by treatment group.

Duration of exposure will be summarized in two ways by treatment group.

- Descriptive statistics for days on therapy.
- Frequencies and percentages of exposure time (in days) as follows:
  - less than 7 days
  - at least 7 days, less than 14 days
  - at least 14 days, less than 28 days
  - at least 28 days, less than 42 days
  - 42 days or more
  - Unknown.

### **7.3.2 Treatment Compliance**

The study treatment administration and compliance profile will be summarized descriptively for each visit and overall for the SAF and displayed in data listings. Summaries for number of pills dispensed during a visit and number of pills taken (number of pills dispensed – returned) will be displayed. Compliance (%) for a particular visit will be calculated as:  $[(\text{number of pills dispensed} - \text{number of pills returned}) / (4 * \text{number of days in the visit period})] * 100$ .

Percent overall compliance will be summarized in two ways for the SAF:

- Descriptive statistics will be presented by treatment group.
- Percent compliance will be categorized according to the following categories by treatment group:
  - less than 50%
  - at least 50%, less or equal to 75%
  - greater than 75%
  - Unknown.

## 7.4 Analysis of Efficacy

All efficacy analyses will be performed on the FAS and PPS.

### 7.4.1 Analysis of Primary Endpoint(s)

The primary efficacy endpoint is time to prostate cancer progression (pathological or therapeutic), and the hypothesis for analysis is:

$H_0$ : The time to progression for Enzalutamide and Active Surveillance (AS) are the

same  $H_1$ : The time to progression for Enzalutamide and AS are not the same

Median and 95% confidence intervals for time to prostate cancer progression (pathological or therapeutic) will be calculated with the Kaplan-Meier (KM) method for each treatment group. Subjects with no cancer progression at the time of trial completion, discontinuation or death will be censored at the last assessment date. Additionally, subjects switching therapy during the study will be censored at the time of the initial therapy switch, but subjects discontinuing therapy will not be censored until the time of study discontinuation. If less than 50% of subjects progress by study cut-off time, the 25th percentile and its two-sided 95% confidence interval will be reported. KM plots will be generated.

Treatment group differences between enzalutamide versus AS will be based on a Cox regression model. The resulting Hazard ratio (enzalutamide/AS) and 95% confidence interval will be included in the summary. Censoring assumptions will follow the same rules as applied for the KM estimates. Fixed effects for the model will include the treatment groups, randomization stratification factors [prostate cancer risk (low/intermediate), type of biopsy performed (mpMRI targeted/non mpMRI targeted)], age, race, and time since prostate cancer diagnosis. Additionally, a random effect of site will be included in the model.

The association between the survival time, log of time to disease progression, and survival probability, log negative log, will be investigated graphically by Cox proportional-hazards models. If the proportional hazards assumption is violated, appropriate remedial methods will be investigated and applied.

Data listings will be provided.

In addition to an overall analysis, the primary and secondary analyses will be repeated for pathological progression and therapeutic progression, individually.

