7. Clinical labs, which will be assessed by the study's central laboratory, include serum chemistries (comprehensive metabolic panel) and hematology (CBC with differential).
8. Serum hormonal levels to be measured are testosterone, DHT, dihydroepiandrosterone, androstenedione and estradiol.
9. Serum PSA will be measured by the study's central laboratory.
10. If warranted per Investigator's clinical opinion or per standard of care.
11. [REDACTED] **CCI** [REDACTED].
12. Biopsies may be done with or without mpMRI targeting. Sites must use a consistent method (either with or without mpMRI targeting) for all of their study subjects. Any biopsy performed during the subject's study participation will be analyzed centrally (for histological reading, [REDACTED] **CCI** [REDACTED]).
13. Biopsy must be done within 6 months prior to the Screening Visit, and submitted for central analysis (histological reading, [REDACTED] **CCI** [REDACTED]). For this biopsy, a minimum of 10 cores is required.
14. Subjects who withdraw from the study prior to the 24m Visit will be asked to complete all subject reported outcomes questionnaires (BFI, SF-12, EPIC, MAX-PC) at their final study visit.
15. Only the urinary, sexual and hormonal domains will be used.
16. Adverse events (serious and non-serious) will be collected from the time the subject signs the consent form until the subject completes the study.
17. Study drug is only applicable to subjects randomized to the enzalutamide arm; subjects randomized to AS will not be dispensed any study drug.
18. Subjects will have the option of having an additional sample collected at each phlebotomy session for storage and analysis in future trials of future trials of biomarker discovery for localized prostate cancer

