**CCI**

#### **3.2 Study Design**

This is a multicenter, randomized, open label exploratory study, conducted in the US and Canada, evaluating the efficacy and safety of enzalutamide for extension of time to prostate cancer progression (pathological or therapeutic) in subjects with clinically localized, histologically proven prostate cancer that is categorized as low risk or intermediate risk and who are under AS. A total of 222 subjects from approximately 50 centers will be enrolled. Subjects are eligible if they were diagnosed within 6 months of screening and have been on AS. A minimum of ten cores from transrectal ultrasound-guided prostate biopsy (mpMRI targeted versus non-mpMRI targeted) are required; confirmatory biopsy before entering the study is not required and is done at the discretion of the investigator.

Low risk is defined as T1c-T2a, PSA $<$ 10, N0, M0 (or presumed N0, M0 if computerized tomography [CT]/bone scan not done due to low risk of metastases), GS  $\leq$  6, ECOG status  $\leq$  2 and estimated life expectancy  $>$  5 years. Intermediate risk is defined as T2b-T2c, PSA $<$ 20, N0, M0 (or presumed N0, M0 if CT/bone scan not done), GS  $\leq$  7 (3+4 pattern only), ECOG status  $\leq$  2 and estimated life expectancy  $>$  5 years.

Prostate cancer progression is defined as either therapeutic progression or pathological progression. Therapeutic progression is defined as the earliest occurrence of primary therapy for prostate cancer (prostatectomy / radiation / focal therapy / systemic therapy). Pathological progression is defined as increase in primary or secondary Gleason pattern by  $>$  1 or higher

proportion of cancer positive cores (>15% increase). Subjects will be stratified by low versus intermediate risk and type of biopsy performed (mpMRI targeted versus non-mpMRI targeted).

Subjects will be randomized (1:1) either to receive treatment with enzalutamide (160 mg), administered as four 40 mg capsules, by mouth, once daily or to AS during the one year study treatment period. Following the one year treatment period, all subjects will be followed for one additional year. Subjects will be followed up every 3 months for these 2 years, after which follow-up will either be every 6 months or unscheduled until the last subject finished their 2 year follow-up. Serum PSA will be measured at baseline and every 3 months during subsequent follow-up visits.

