Progression-free survival is defined as the time (in months) from the date of randomization until the date of the cancer progression (pathological or therapeutic). Pathological progression is defined as increase in primary or secondary Gleason pattern by  $\geq 1$  or higher proportion of cancer positive cores ( $\geq 15\%$  increase). Therapeutic progression is defined as the earliest occurrence of primary therapy for prostate cancer (prostatectomy/radiation/focal therapy/systemic therapy).

Subjects with no cancer progression at the time of trial completion (the last study-wide subject completes a 24 month follow-up visit), discontinuation or death will be censored at the last assessment date. Subjects discontinuing therapy will not be censored until the time of study discontinuation. Additionally, subjects switching therapy during the study will be censored at the time of the initial therapy switch.

For subjects on enzalutamide, TEAEs, defined as an adverse event observed after starting administration of the study drug and until 30 days after treatment end date, are categorized as AEs. If the adverse event occurs on Day 1 and the onset check box is marked “Onset after first dose of study drug” or the onset check box is left blank, then the adverse event will be considered treatment emergent. If the adverse event occurs on Day 1 and the onset check box is marked “Onset before first dose of study drug”, then the adverse event will be categorized as medical history. If a subject experiences an event both during the pre-investigational period and during the investigational period, the event will be considered as an AE only if it has worsened in severity (i.e. it is reported with a new start date). All adverse events collected that begin within 30 days following study discontinuation will also be counted.

Percent positive cores are calculated using the number of systemically-sampled prostate regions and any targeted regions with at least one positive core divided by the total number of systematically-sampled regions and targeted regions. This implies that despite the number of samples within a given systematic or targeted region, any positive core will indicate that region as positive.

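### The therapy-switch censoring rule is not separated from therapeutic progression, so an event of the primary endpoint can be coded as a censored time

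*SAP*

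**What the plan says.** **The event.** The primary endpoint is time to pathological or therapeutic progression. Section 3.2 states: "Therapeutic progression is defined as the earliest occurrence of primary therapy for prostate cancer". It lists prostatectomy, radiation, focal therapy and systemic therapy, and Section 6.4 repeats the definition.

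**The general censoring rule.** Section 7.4.1: "Subjects with no cancer progression at the time of trial completion, discontinuation or death will be censored at the last assessment date". This sentence is expressly limited to subjects who have not progressed.

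**The switch rule.** The next sentence of Section 7.4.1 opens with the word 'Additionally' and provides that "subjects switching therapy during the study will be censored at the time of the initial therapy switch, but subjects discontinuing therapy" are kept under observation until they leave the study. Section 6.4 has the same rule: "subjects switching therapy during the study will be censored at the time of the initial therapy switch". Neither place repeats the limit to subjects without progression, defines a switch, or gives an order of precedence.

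**Where the rule applies.** For the Cox model, Section 7.4.1 says: "Censoring assumptions will follow the same rules as applied for the KM estimates". Section 7.4.1.2 brings the same rules into the subgroup analyses. Sections 7.4.1 and 7.4.1.1 repeat the analyses for pathological and therapeutic progression separately. The incidence analysis in Section 7.4.1.1 states no switch censoring.

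**The concern.** A subject who leaves the assigned management for surgery, radiation, focal therapy or another systemic therapy meets two rules on the same date. Under one, that date is an event. Under the other, it is a censoring time. The SAP does not say which applies.

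Two programmers could therefore derive different primary event counts from the same data. The conflict is sharpest in the therapeutic-only analysis, where the act that triggers censoring can be the endpoint itself. The trial is open label, so the choice to start therapy may depend on the assigned arm. Censoring at that point would then probably be informative. If the literal reading were programmed, the incidence counts in Section 7.4.1.1 could also differ from the Kaplan-Meier counts, and the SAP does not say which count governs.

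**Working it through.** **1. What is left for the switch rule to act on.**
- Stopping therapy is handled in the other half of the same sentence and does not censor, so a switch must mean starting something else.
- For these subjects the natural candidates are the therapies on the event list, and that list includes systemic therapy as a whole.
- The SAP names no change of therapy that would be a switch but not an event. The overlap is therefore close to the whole content of the rule.
- A subject with an earlier pathological event keeps that event if events are taken in date order.

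**2. Reproducing the plan's figure.** Inputs from Section 4: 222 subjects randomised 1:1, one year of accrual, three years in total, 16% loss to follow-up, annual rates 0.2310 and 0.1189, two-sided 5%, 80% power, 72 events.

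- Hazard ratio: 0.1189/0.2310 = 0.5147; |ln 0.5147| = 0.6641.
- Required events (Schoenfeld): 4 × (1.960 + 0.842)² / 0.6641² = 71.2, rounded up to 72.
- Power at 72 events: Φ(√72/2 × 0.6641 − 1.960) = Φ(0.858) = 80.4%.
- Expected events: 16% loss is taken as exponential over three years (an assumption), so the loss rate is −ln(0.84)/3 = 0.0581. With h equal to the event rate plus 0.0581, events per arm = 111 × (rate/h) × [1 − (e^(−2h) − e^(−3h))/h].
  - AS: h = 0.2891, giving 45.5.
  - Enzalutamide: h = 0.1770, giving 26.6.
  - Total: 72.1, which agrees with the plan.

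**3. Illustration: equal loss in both arms.** Let a share s of all events be recoded as censored, with the hazard ratio unchanged at 0.5147. The SAP gives no split of events, so s is an assumption. Power = Φ(√(72(1 − s))/2 × 0.6641 − 1.960).

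| s | Events left | Power |
|---|---|---|
| 0 | 72 | 80.4% |
| 10% | 64.8 (about 65) | 76.2% |
| 30% | 50.4 (about 50) | 65.4% |

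**4. Illustration: the hazard ratio need not stay the same.** Suppose 20% of the AS rate is therapeutic (0.0462) and 80% pathological (0.1848), and that all therapeutic events are censored in both arms. The overall rates stay as planned.

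- If the therapeutic hazard ratio is 0.3, the pathological rate on enzalutamide is 0.1189 − 0.3 × 0.0462 = 0.1050. The remaining ratio is 0.1050/0.1848 = 0.57.
- If the therapeutic hazard ratio is 1.0, that rate is 0.1189 − 0.0462 = 0.0727. The remaining ratio is 0.0727/0.1848 = 0.39.

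Against a composite of 0.51, the estimate can move in either direction.

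**The case against.** The best defence is that 'Additionally' follows directly on a sentence about subjects without progression, so the switch rule can be read as a further rule for that group. On that reading, starting a listed therapy is always an event and nothing is lost. It is also the only reading that leaves the planned therapeutic-only analysis intact, and a careful programmer may well adopt it. This stands as a plausible reading, but it is not written: the switch sentence has its own subject and no limit. It would also leave the rule with almost nothing to do.

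It can also be said that the study is labelled exploratory and that a protocol may define the term. Neither removes the point. Event and censoring derivation belongs in an SAP, and this one addresses it twice without pointing to a definition elsewhere.

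A reader might go further and infer a bias in favour of enzalutamide. Table 2, footnote 17, says "subjects randomized to AS will not be dispensed any study drug", so perhaps only enzalutamide subjects can switch, and only during the treatment year. Their therapy starts would then be censored while those on AS count. The SAP does not support that as a finding:

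- A move from surveillance to surgery or radiation can equally be called a switch, which brings in both arms.
- A subject who stops enzalutamide and later starts a listed therapy is arguably covered by the discontinuation half of the sentence and would count as an event.
- The constant-rate model puts 111 × (0.1189/0.1770) × (1 − e^(−0.1770)) = 12.1 enzalutamide events in the first year, but that takes everyone as on drug throughout and includes pathological events. Scheduled biopsies come at 12 and 24 months, and biopsy is recommended when intervention is considered, so many of these may be pathological.

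**Conclusion.** The conflict is real and should be fixed. The SAP makes the first listed therapy an event and also censors at an undefined therapy switch, with no limit to subjects without progression and no precedence rule. Read literally, it can recode events in the composite Kaplan-Meier and Cox analyses and in the subgroup analyses, and it can undercut the therapeutic-only analysis.

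The size is not known. The fall in power from 80% to between 76% and 65% rests on assumed shares of 10% to 30%, equal loss in both arms and an unchanged hazard ratio. Loss in one arm only would bias the hazard ratio. Which arms are affected, which way the estimate would move, and whether the type I error would rise all depend on the meaning of switch and on the share of therapeutic events. The SAP gives neither, so no claim of a particular direction or of a particular inflated error rate is justified.

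**What to change.** In Sections 6.4 and 7.4.1:

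1. State that, for the composite and therapeutic-only endpoints, the start of any listed primary therapy other than the assigned study drug is an event on its start date, in either arm, and takes precedence over censoring.
2. Either drop switch censoring from these analyses, or define a switch so that it excludes the listed therapies and limit the rule to subjects with no earlier progression.
3. Leave the other censoring rules as they are.

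The cost is one definition, one precedence sentence and one line in the event derivation. No new data are needed, because therapies are already reviewed at study visits (Table 2 and Section 7.3.1). The change affects analysis coding only, not the management of subjects.
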